### **Adverse events**

#### *Start date*

If only the year is known, the complete date will be assumed to be January 1st of the given year. If both month and year are known, the complete date will be assumed to be the 1st of the given month.

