7.2 Handling of Safety Parameters

7.2.1 Reporting of Adverse Events

After informed consent, but prior to initiation of study medication, only SAEs caused by a protocol-mandated intervention will be collected (e.g., SAEs related to invasive procedures such as biopsies, medication washout, or no treatment run-in).

All AEs (regardless of relationship to the study medication), occurring during the study and until 28 days after the last study drug administration (safety follow-up visit) must be reported in the AE eCRF.

All AEs related with the study medication occurring during the study and until the last visit of the survival follow-up period must be reported in the AE eCRF.

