### **5.3.10.5 Adverse events**

Adverse event (AE) data will be presented in frequency tables (overall, by grade (1, 2, 3, 4, or 5), by severity (mild, moderate, severe, life threatening or disabling or death related), by relationship (unrelated, remote relation, possible relation or probable relation) and by action taken (dose changed, interrupted, withdrawal or none). In tables showing the incidence of adverse events, subjects who experienced the same event on more than one occasion are counted only once in the calculation of the event frequency.

For selected events of particular interest, such as Stevens-Johnson syndrome and interstitial lung disease, summary tables will be presented for time to first onset of the event and for the total number of episodes. Every occurrence of an event in any subject will be counted in the total number of episodes but successive reports of an identical event in the same phase (treatment, follow-up) will be combined (concatenated) into a one episode if the end date of the earlier event was the same as the start date of the later event, or if the end date of the earlier event was missing.

A listing of adverse events by patient, whose adverse events led to withdrawal of study treatment or to dose modification will be done. In case of deaths, a brief narrative describing each death will be done.

All AEs and laboratory variables will be assessed according to the NCI CTC-AE version 4.0 grading system.

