#### Medication and adverse events

**Duration of adverse event:** The interval between the start and end or patient worsened in severity or death dates of the adverse event in days.

**Time to first onset (Interstitial lung disease):** Time between baseline visit and first occurrence of Interstitial lung disease, in weeks, within patients with this adverse event.

**Time to first onset (Stevens-Johnson syndrom):** Time between baseline visit and first occurrence of Stevens-Johnson syndrom, in weeks, within patients with this adverse event.

**Duration of study drug dispensability:** The interval between the dispensed medication date at baseline and the returned medication date at the end of study treatment visit in weeks.

**Drug compliance:** The ratio of used units (tablets) (dispensed at a visit) to number of days between visits. In case the prescribed dose is 50mg, the denominator of this ratio will be multiplied by two.

**Weighted average doses:** the weighted average doses of each patient will be calculated according to the following formula

$$\frac{(150mg \times \text{days on dose } 150mg) + (100mg \times \text{days on dose } 100mg) + (50mg \times \text{days on dose } 50mg)}{\text{total number of days taking medication}}$$

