#### *End date*

If only the year is known, the complete date will be assumed to be December 31st of the given year. If both month and year are known, the complete date will be assumed to be the last day of the given month.

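### Partial adverse-event dates are completed with no floor at baseline and no cap at death or last contact, so some on-treatment events can be dated before first dose or listed as over-long

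*SAP*

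**What the plan says.** SAP section 5.4 refers every incomplete date to Appendix 4, so that appendix is the only source of rules.

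- **Start of an adverse event:** "If only the year is known, the complete date will be assumed to be January 1st of the given year". For month-level information: "If both month and year are known, the complete date will be assumed to be the 1st of the given month".
- **End of an adverse event:** "If only the year is known, the complete date will be assumed to be December 31st of the given year". For month-level information, "the complete date will be assumed to be the last day of the given month".
- **Death:** a death known to the month goes to the 1st of that month. A death known only by year is tied to the last contact when the two years agree. This is the only place in Appendix 4 where another known date limits an imputed one.

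The imputed dates feed two derived variables in Appendix 3. Time to first onset is defined for ILD as "Time between baseline visit and first occurrence of Interstitial lung disease, in weeks, within patients with this adverse event", with a matching definition for Stevens-Johnson syndrome, and is shown in Tables 37 and 38. Duration is derived for every adverse event and appears in Listing 4. Its definition names the event's end, a worsening and death as possible end points, but does not say that the earliest applies.

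The date of first dose is not on the CRF. SAP section 5.3.9.2 takes the baseline visit in its place (stated for overall survival). Protocol section 7.2.1 adds that, "prior to initiation of study medication, only SAEs caused by a protocol-mandated intervention will be collected".

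**The concern.** The start rule always picks the earliest possible day and the end rule always picks the latest. Neither looks at what else is known about the patient. If treatment began mid-month and the site records only the month of onset, the rule puts the event before treatment even when it clearly happened on treatment. Onsets in the baseline month are realistic here: protocol section 6.1 reports rash in the first several days of erlotinib in more than half of patients.

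At stake are the onset times in Tables 37 and 38, and the start dates, end dates and durations in Listing 4. A value would be wrong because of a stated rule, although the study already holds the dates needed to prevent it. The same omission lets the adverse-event end rule and the death rule give different dates for one fatal event.

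**Working it through.** The plan states no figure that depends on these rules, so there is none to reproduce. The rules are applied by calendar arithmetic. Calendar years and dates in the examples are illustrative.

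**1. Onset time = imputed start - baseline visit.**
- Baseline 20 March, start known as March: 1 March - 20 March = -19 days (-19/7 = -2.7 weeks).
- Baseline 20 September of a 365-day year, start known by year only: 1 January - 20 September = -262 days (-37.4 weeks).
- All 365 baseline dates, partial start in the baseline month: 0 to -30 days. The value is negative unless baseline is the 1st of a month: (365 - 12)/365 = 353/365 = 96.7%.
- Year only, in the baseline year: 0 to -364 days, negative for 364/365 = 99.7%.
- Outside the baseline month (or year) the start still moves earlier, but not to before baseline.

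**2. How often a partial start goes negative.** The documents give neither the number of partial dates nor an onset distribution. Assume true onset is uniform over H days after baseline:

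| H (days) | Month known | Year only |
|---|---|---|
| 56 | 26% | 92% |
| 90 | 16% | 88% |
| 180 | 8% | 75% |
| 365 | 4% | 50% |

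Assuming instead exponential onset with medians of 14, 28, 56 and 84 days gives 47, 29, 16 and 11% (month known) and about 94, 89, 78 and 69% (year only). All of these are shares of events that already have a partial start.

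**3. Reach into Tables 37 and 38.** Protocol section 7.3 gives ILD-like events at about 0.6% overall, and serious ones at 0.8% in the pivotal study. Expected cases in 30 patients: 30 × 0.006 = 0.18 to 30 × 0.008 = 0.24. Chance of at least one: 1 - 0.994^30 = 17% to 1 - 0.992^30 = 21%. The protocol calls cases suggestive of Stevens-Johnson syndrome very rare and gives no rate.

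**4. Duration = imputed end - imputed start.** With both dates partial in one month, the result is 27 to 30 days whatever the truth. With both year-only in one year, it is 364 days (365 in a leap year). These two rules alone never give a negative duration.

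**5. Fatal event, month known (April 2012).** Adverse-event end 30 April; imputed death 1 April; gap 29 days. If the death is fully known as 5 April, the event still ends 30 - 5 = 25 days after it.

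**6. Interim cut-off, 30 September 2013.** A month-only end in September 2013 becomes 30 September, 0 days past. A year-only 2013 end becomes 31 December, 31 + 30 + 31 = 92 days past.

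**7. Effect of bounding.** Baseline 20 March 2012; true event 25 to 28 March (onset day 5, duration 3 days); for the year-only row, death assumed on 5 April 2012.

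| Known | Current onset / duration | Bounded onset / duration |
|---|---|---|
| Month | -19 / 30 days | 0 / 11 days |
| Year | -79 / 365 days | 0 / 16 days |

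**The case against.** The strongest reply is that almost nothing reported depends on this. Onset time is derived for only two rare events, and both must reach the sponsor within 24 hours (protocol section 7.2.2), so their onset day is unlikely to be missing. Duration appears only in a by-patient listing. Earliest start with latest end is a recognisable longest-duration convention. Validation checks and source verification (protocol section 9) reduce partial dates further. All of this stands as a limit on size. It does not justify a rule that overrides dates already held.

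A reader might infer more than the documents support:

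- **Every imputed pre-baseline onset is false.** No. Section 7.2.1 of the protocol does collect procedure-caused serious events before dosing, and screening covers days -21 to -1, so an early onset in the baseline month can be genuine.
- **Imputed ends overrun the interim cut-off generally.** Only year-only ends can. The adverse-event outputs named for the interim in SAP section 6.12 include neither Tables 37 and 38 nor Listing 4.
- **Incidence or efficacy is distorted.** The SAP has no treatment-emergent filter, so an early imputed start drops no event from the incidence tables. Response, PFS and OS do not use adverse-event dates.
- **Episodes are double-counted.** Records are joined "if the end date of the earlier event was the same as the start date of the later event" (or if the earlier end is missing). Two month-only records in one month would be imputed to its last and first days and would not match. But sharing a month does not show that the true dates coincided. Matching on month or year would merge distinct events, for example one ending in February with another starting in November.

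**Conclusion.** The point holds as a minor defect in the SAP. The imputation for adverse-event dates has no floor at baseline and no cap at death or last contact. An on-treatment event with a partial start in the baseline month or year can be dated before first dose by up to 30 days (month known) or 364 days (year only, 365-day year). This would give a negative onset time only for ILD or Stevens-Johnson syndrome, where few or no cases are expected. For other events it gives wrong start dates and over-long, not negative, durations in Listing 4. For fatal events known only by month, the end and death rules disagree by the length of the month less one day.

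The mechanism and per-event sizes follow from the text and the calendar. The shares of events affected rest on assumed onset distributions, and the total effect cannot be stated because the number of partial dates is not given. Efficacy conclusions and incidence tables are unaffected by the adverse-event rules.

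**What to change.** Amend SAP Appendix 4 as follows.

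1. **Start.** Impute the baseline visit date when three conditions hold: the known month and year (or the year alone) match the baseline visit; the event is not recorded as a pre-treatment, procedure-related serious event; and any known end date is not before baseline. Otherwise keep the current rule. The conditions matter. For a biopsy-related event known to start in March 2012 and end on 12 March, with baseline on 20 March, an unconditional floor would give 12 - 20 = -8 days.
2. **End.** Use the earliest of the current imputed date, death and last contact (and, for year-only dates at the interim, the data cut-off), never earlier than the start.
3. **Fatal events.** State one date to serve as both the event's end and the death. The cap alone is not enough: with a known start of 15 April and both end and death known only as April, the cap gives 1 April, the start condition moves it to 15 April, and the event still ends 14 days after the imputed death. If the reconciliation moves an imputed death date, that patient's survival time moves too, so settle it before database lock.

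Leave the episode rule in SAP section 5.3.10.5 unchanged.

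The cost is a few sentences of SAP text and the matching lines of derivation code. No new data are needed.

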#### *End date*

If only the year is known, the complete date will be assumed to be December 31st of the given year. If both month and year are known, the complete date will be assumed to be the last day of the given month.

# Appendix 5: The RECIST Criteria for Tumor Response

## Response Evaluation Criteria in Solid Tumors (RECIST) Version 1.1

Quick Reference (<http://ctep.cancer.gov/guidelines/recist.html>)

### Measurability of tumor at baseline

#### 1. Definitions

At baseline, tumor lesions/lymph nodes will be categorized measurable or non-measurable as follows:

##### 1.1. Measurable

Tumor lesions: Must be accurately measured in at least one dimension (longest diameter in the plane of measurement is to be recorded) with a minimum size of:

- 10 mm by CT scan (CT scan slice thickness no greater than 5 mm).
- 10 mm caliper measurement by clinical exam (lesions which cannot be accurately measured with calipers should be recorded as non-measurable).
- 20 mm by chest X-ray.

Malignant lymph nodes: To be considered pathologically enlarged and measurable, a lymph node must be P15mm in short axis when assessed by CT scan (CT scan slice thickness recommended to be no greater than 5 mm). At baseline and in follow-up, only the short axis will be measured and followed.

##### 1.2. Non-measurable

All other lesions, including small lesions (longest diameter <10 mm or pathological lymph nodes with P10 to <15 mm short axis) as well as truly non-measurable lesions. Lesions considered truly non-measurable include: leptomeningeal disease, ascites, pleural or pericardial effusion, inflammatory breast disease, lymphangitic involvement of skin or lung, abdominal masses/abdominal organomegaly identified by physical exam that is not measurable by reproducible imaging techniques.

##### 1.3. Special considerations regarding lesion measurability

Bone lesions, cystic lesions, and lesions previously treated with local therapy require particular comment:

Bone lesions:

- Bone scan, PET scan or plain films are not considered adequate imaging techniques to measure bone lesions. However, these techniques can be used to confirm the presence or disappearance of bone lesions.

- Lytic bone lesions or mixed lytic-blastic lesions, with identifiable soft tissue components, that can be evaluated by cross sectional imaging techniques such as CT or MRI can be considered as measurable lesions if the soft tissue component meets the definition of measurability described above.

- Blastic bone lesions are non-measurable.

Cystic lesions:

- Lesions that meet the criteria for radiographically defined simple cysts should not be considered as malignant lesions (neither measurable nor non-measurable) since they are, by definition, simple cysts.

- 'Cystic lesions' thought to represent cystic metastases can be considered as measurable lesions, if they meet the definition of measurability described above. However, if noncystic lesions are present in the same patient, these are preferred for selection as target lesions.

Lesions with prior local treatment:

- Tumor lesions situated in a previously irradiated area, or in an area subjected to other loco-regional therapy, are usually not considered measurable unless there has been demonstrated progression in the lesion. Study protocols should detail the conditions under which such lesions would be considered measurable.

## **2. Specifications by methods of measurements**

### **2.1. Measurement of lesions**

All measurements should be recorded in metric notation, using calipers if clinically assessed. All baseline evaluations should be performed as close as possible to the treatment start and never more than 4 weeks before the beginning of the treatment.

### **2.2. Method of assessment**

The same method of assessment and the same technique should be used to characterize each identified and reported lesion at baseline and during follow-up. Imaging based evaluation should always be done rather than clinical examination unless the lesion(s) being followed cannot be imaged but are assessable by clinical exam.

Clinical lesions: Clinical lesions will only be considered measurable when they are superficial and P10mm diameter as assessed using calipers (e.g. skin nodules). For the case of skin lesions, documentation by color photography including a ruler to estimate the size of the lesion is suggested. As noted above, when lesions can be evaluated by both clinical exam and imaging, imaging evaluation should be undertaken since it is more objective and may also be reviewed at the end of the study.

Chest X-ray: Chest CT is preferred over chest X-ray, particularly when progression is an important endpoint, since CT is more sensitive than X-ray, particularly in identifying new lesions. However, lesions on chest X-ray may be considered measurable if they are clearly defined and surrounded by aerated lung.

CT, MRI: CT is the best currently available and reproducible method to measure lesions selected for response assessment. This guideline has defined measurability of lesions on CT scan based on the assumption that CT slice thickness is 5 mm or less. When CT scans have slice thickness greater than 5 mm, the minimum size for a measurable lesion should be twice the slice thickness. MRI is also acceptable in certain situations (e.g. for body scans).

Ultrasound: Ultrasound is not useful in assessment of lesion size and should not be used as a method of measurement. Ultrasound examinations cannot be reproduced in their entirety for independent review at a later date and, because they are operator dependent, it cannot be guaranteed that the same technique and measurements will be taken from one assessment to the next. If new lesions are identified by ultrasound in the course of the study, confirmation by CT or MRI is advised. If there is concern about radiation exposure at CT, MRI may be used instead of CT in selected instances.

Endoscopy, laparoscopy: The utilization of these techniques for objective tumor evaluation is not advised. However, they can be useful to confirm complete pathological response when biopsies are obtained or to determine relapse in trials where recurrence following complete response or surgical resection is an endpoint.

Tumor markers: Tumor markers alone cannot be used to assess objective tumor response. If markers are initially above the upper normal limit, however, they must normalize for a patient to be considered in complete response. Because tumor markers are disease specific, instructions for their measurement should be incorporated into protocols on a disease specific basis.

Cytology, histology: These techniques can be used to differentiate between PR and CR in rare cases if required by protocol (for example, residual lesions in tumor types such as germ cell tumors, where known residual benign tumors can remain). When effusions are known to be a potential adverse effect of treatment (e.g. with certain taxane compounds or angiogenesis inhibitors), the cytological confirmation of the neoplastic origin of any effusion that appears or worsens during treatment can be considered if the measurable tumor has met criteria for response or stable disease in order to differentiate between response (or stable disease) and progressive disease.

### **Tumor response evaluation**

#### **1. Assessment of overall tumor burden and measurable disease**

To assess objective response or future progression, it is necessary to estimate the overall tumor burden at baseline and use this as a comparator for subsequent measurements. Only patients with measurable disease at baseline should be included in protocols where objective tumor response is the primary endpoint. Measurable disease is defined by the presence of at least one measurable lesion. In studies where the primary endpoint is tumor progression (either time to progression or proportion with progression at a fixed date), the protocol must specify if entry is restricted to those with measurable disease or whether patients having non-measurable disease only are also eligible.

## 2. Baseline documentation of 'target' and 'non-target' lesions

When more than one measurable lesion is present at baseline all lesions up to a maximum of five lesions total (and a maximum of two lesions per organ) representative of all involved organs should be identified as target lesions and will be recorded and measured at baseline (this means in instances where patients have only one or two organ sites involved a maximum of two and four lesions respectively will be recorded).

Target lesions should be selected on the basis of their size (lesions with the longest diameter), be representative of all involved organs, but in addition should be those that lend themselves to reproducible repeated measurements. It may be the case that, on occasion, the largest lesion does not lend itself to reproducible measurement in which circumstance the next largest lesion which can be measured reproducibly should be selected.

Lymph nodes merit special mention since they are normal anatomical structures which may be visible by imaging even if not involved by tumor. Pathological nodes which are defined as measurable and may be identified as target lesions must meet the criterion of a short axis of  $\geq 15$  mm by CT scan. Only the short axis of these nodes will contribute to the baseline sum. The short axis of the node is the diameter normally used by radiologists to judge if a node is involved by solid tumor. Nodal size is normally reported as two dimensions in the plane in which the image is obtained (for CT scan this is almost always the axial plane; for MRI the plane of acquisition may be axial, sagittal or coronal). The smaller of these measures is the short axis. For example, an abdominal node which is reported as being 20 mm·30 mm has a short axis of 20 mm and qualifies as a malignant, measurable node. In this example, 20 mm should be recorded as the node measurement. All other pathological nodes (those with short axis  $\geq 10$  mm but  $< 15$  mm) should be considered non-target lesions. Nodes that have a short axis  $< 10$  mm are considered non-pathological and should not be recorded or followed. A sum of the diameters (longest for non-nodal lesions, short axis for nodal lesions) for all target lesions will be calculated and reported as the baseline sum diameters. If lymph nodes are to be included in the sum, then as noted above, only the short axis is added into the sum. The baseline sum diameters will be used as reference to further characterise any objective tumor regression in the measurable dimension of the disease.

All other lesions (or sites of disease) including pathological lymph nodes should be identified as non-target lesions and should also be recorded at baseline. Measurements are not required and these lesions should be followed as 'present', 'absent', or in rare cases 'unequivocal progression'. In addition, it is possible to record multiple nontarget lesions involving the same organ as a single item on the case record form (e.g. 'multiple enlarged pelvic lymph nodes' or 'multiple liver metastases').

